7.1 DEMOGRAPHIC AND OTHER BASELINE CHARACTERISTICS

Only descriptive statistics are planned for this section of the report. All baseline analyses will be done for the prescribed patient set.

7.2 CONCOMITANT DISEASES AND MEDICATION

Only descriptive statistics are planned for this section of the report. All analyses will be done for the prescribed patient set.

7.3 PRIMARY OUTCOME

For the primary outcome, the baseline characteristics will be analysed in a descriptive manner. Frequencies and 95% CI will be given when appropriate.

In addition the baseline characteristics will be compared by medication, physician speciality and country using χ^2 -Test or Fisher's exact test, if χ^2 -Test is not valid, for categorical variables and Wilcoxon-Mann-Whitney test for continuous variables.

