9.2 SETTING

Data collection from approximately 4000 patients from up to 8 countries is planned. Site selection will be performed to reflect routine T2D care in the participating countries in order to secure representativeness of the T2D population. The following countries will participate in this non-interventional study: Bulgaria, Czech Republic, Hungary, Poland, Russia, Serbia, Slovenia.

A log of all patients included into the study (i.e. having given informed consent) will be maintained in the Investigator Site File (ISF).

Boehringer Ingelheim reserves the right to discontinue the study or to remove a patient at a particular study site for the following reasons:

1. Failure to meet expected enrollment goals overall or at a particular study site.
2. Emergence of any efficacy/safety information that could significantly affect continuation of the study, or any other administrative reasons, i.e. lack of recruitment.
3. Violation of the protocol, the contract, or applicable laws and regulations for non-interventional studies, which could disturb the appropriate conduct of the NIS.

Site selection:

Office based HCP of different medical specialties (endocrinologist, diabetologist or cardiologist) will be requested in order to check for feasibility prior to site selection. Amongst other criteria, sites will be eligible if HCPs have access and can prescribe at least 2 of the T2D drug classes of interest (SGLT2i, DPP4i and/or GLP1a). Sites will also be asked for the number of expected patients meeting inclusion/exclusion criteria in a given time window (1 month September 2018) by means of being newly initiated with empagliflozin or other SGLT2i, DPP4i or GLP1a in September 2018. In case that more than a representative number of sites which will be assessed during the feasibility, are signaling their willingness to participate in the study, the sites will be randomly selected.

To get basic information into demographics for site distribution, data on physicians' age, gender, office postal code will be collected.

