9.3.2 Outcomes

1. Patient demographics:

- age
- gender
- height
- weight
- BMI
- Ethnicity*

*assessment of ethnicity (black or non-black) necessary for calculation of eGFR

2. Time since diagnosis of Type 2 Diabetes (years)

3. Clinical parameters relevant for T2D, CVD, CKD assessment (last available and date when it was collected) as valid on study index date 1

- T2D
 - HbA1c (numeric value)
- CVD
 - Blood pressure (numeric value for systolic and diastolic blood pressure)
 - LVEF (numeric value and info on whether an Echo was performed)
 - Blood lipids (numeric values for total cholesterol, LDL, HDL, and triglycerides)
- CKD
 - Serum creatinine (numeric value)
 - eGFR (calculated for analysis according to the CKD-EPI formula considering serum creatinine level, gender, age, and ethnicity)
 - UACR (numeric value)

4. Prevalence of comorbidities and related risk factors for CVD, CKD at index date 1

- Comorbidities
 - History of acute myocardial infarction (yes/no)
 - History of cardiology intervention (such as Percutaneous Coronary Intervention (PCI), Coronary Artery Bypass Grafting (CABG)) (yes/no)
 - Ischemic heart disease (defined as coronary artery disease, angina) (yes/no)
 - Heart failure (yes/no)
 - Confirmed by echocardiography (yes/no)
 - History of stroke (yes/no)

- Peripheral arterial disease (including limb angioplasty, stenting, bypass surgery, amputation, significant peripheral artery stenosis,) (yes/no)
- Risk factors
 - Being overweight (BMI ≥ 25 to <30) (yes/no) or obese (BMI ≥ 30) (yes/no) according to the WHO criteria (26)
 - Hypertension (defined as systolic blood pressure ≥ 140 mmHg and / or diastolic blood pressure ≥ 90 mmHg) (y/n)
 - 10-year Risk for fatal CVD according to the applying SCORE Risk Chart (European Society of Cardiology) taking into account patient's age, gender, systolic blood pressure, smoking status, and total cholesterol value at index date.
 - Tobacco smoking (current smoker/ ex-smoker/ never smoker)
 - Being physically inactive (defined as less than 2.5 hours of moderate-intensity aerobic exercise or less than 75 minutes of vigorous aerobic exercise per week) (yes/no)
 - Having a family history of early heart disease (yes/no)
 - Having a family history of early kidney disease (yes/no)

5. T2D medication the treating physician newly prescribes at study index date 1 and reason for the choice

- SGLT2i
 - canagliflozin
 - dapagliflozin
 - empagliflozin
 - ertugliflozin
- DPP4i
 - alogliptin
 - linagliptin

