9.5 STUDY SIZE

No formal sample size calculation is provided for this study. This NIS has been designed to describe, in a real-world setting, usage patterns and outcomes associated with empagliflozin or other SGLT2i or DPP4i or GLP1a in the clinical routine practice. The sample size of approximately 4000 patients is driven by the need to enroll an adequate number of patients to address the mentioned objectives, also across various subgroups, such as physician or country specific analyses. It is aspired to document at least 500 patients in the GLP1a and at least 1000 patients each in the SGLT2i and DPP4i subgroups. However, no formal limitations will be applied for recruitment of patients to subgroups with regard to medication of interest.

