7. PLANNED ANALYSES

All patients who have received a first prescription of respective study medication will be included in the analysis; this is the prescribed patient set. All analyses at index date 1 will be performed on the prescribed patient set and analyses at index date 2 will be performed on the full analysis set. If patients have missing values for an outcome, those patients will be excluded for that outcome's analysis.

The assessment will be carried out using SAS® software. The statistical characteristics presented in the end-of-text tables will be N / mean / SD / min / median / max for continuous variables. Tabulations of relative and absolute frequencies will be presented for categorical variables. Incidence rates and 95% CI will be given when appropriate. Subgroup analyses e.g. according to medication (i.e. empagliflozin or SGTL2i or DPP4i or GLP-1 RA), country and physician specialty are planned, as well as per history of CV disease. Descriptive analyses will be supplemented using χ^2 -test or Fisher's exact test for categorical variables and Wilcoxon-Mann-Whitney test for continuous variables. The analyses are purely explorative, hence no correction for multiple testing is needed.

The analyses will relate to the following data as recorded in the eCRF:

1. Patient demographics (age, gender, height, weight, BMI, ethnicity)
2. Time since diagnosis of Type 2 Diabetes
3. Clinical parameters relevant for T2D, CVD, CKD assessment as valid on index date 1
4. Presence of cardiovascular disease and related risk factors at index date 1
5. Presence of chronic kidney disease and related risk factors at index date 1
6. T2D medication the treating physician newly prescribes at study index date 1
7. Reason(s) for treatment decision at index date 1
8. Concomitant T2D medications at study index date 1
9. Concomitant CVD and CKD medications at index date 1
10. Other HCPs involved in treatment decisions at study index date 1 and at index date 2
11. Relevant socioeconomic parameters
12. Discontinuation rate, reason for discontinuation, duration of T2D therapy after one year (± 2 months)

All adverse events and adverse drug reactions collected per study protocol will be included and summarized in the final study report.

For the main analysis data from research question 1 to 5 will be evaluated in a descriptive manner for the total number of prescribed patients enrolled in the study.

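### SAP 7.3 names only a two-sample test (Wilcoxon-Mann-Whitney) for continuous baseline variables compared across factors with three to seven groups, and no readable text says which groups are paired

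*SAP*

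**What the plan says.** SAP 7.3 first describes the primary outcome and then adds a comparison: "the baseline characteristics will be compared by medication, physician speciality and country". Categorical variables get a chi-square or Fisher test. For continuous variables the only test is the one in "for categorical variables and Wilcoxon-Mann-Whitney test for continuous variables". SAP 7, protocol 9.7.1 and the data analysis part of the protocol abstract name the same single test for continuous data.

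The levels of the three factors are found elsewhere:

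- **Medication:** SAP 7 lists four groups: "Subgroup analyses e.g. according to medication (i.e. empagliflozin or SGTL2i or DPP4i or GLP-1 RA), country and physician specialty are planned". By drug class there would be three.
- **Specialty:** protocol 9.2 gives three: "Office based HCP of different medical specialties (endocrinologist, diabetologist or cardiologist".
- **Country:** protocol 9.2 names seven: "Bulgaria, Czech Republic, Hungary, Poland, Russia, Serbia, Slovenia". Another sentence in the same section allows up to 8.

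SAP 7 sets the status of all these tests: "The analyses are purely explorative, hence no correction for multiple testing is needed". SAP 7.1 says that the section on demographic and other baseline characteristics will hold descriptive statistics only.

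**The concern.** Wilcoxon-Mann-Whitney takes exactly two samples, and none of the three factors in SAP 7.3 has two levels. To run the test, someone must decide between all pairs, each level against the rest, one reference group, or a single pooled contrast. No readable text makes that decision or names a k-sample rank test. The other tests in the SAP do not have this problem: chi-square, Fisher and log-rank all accept more than two groups. Wilcoxon-Mann-Whitney does fit history of CV disease, the two-level factor mentioned in SAP 7.

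The choice belongs in the SAP, because the protocol abstract and protocol 9.7 leave statistical detail to the analysis plan. Left open, the number of p-values reported for the primary outcome, and the comparisons they refer to, can be settled after the data are seen.

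**Working it through.** The plan states no alpha, power or test count for these comparisons, so there is no figure of its own to reproduce. The check counts tests under each reading and then illustrates what the choice does to chance findings.

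**1. Tests per continuous variable.** For a factor with k levels, all pairs is k(k−1)/2, level against rest is k, one reference group is k−1, and one overall test is 1.

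| Reading | Medication (k=4) | Specialty (k=3) | Country (k=7) | Total |
|---|---|---|---|---|
| All pairs | 6 | 3 | 21 | 30 |
| Level against rest | 4 | 3 | 7 | 14 |
| One reference group | 3 | 2 | 6 | 11 |
| One overall test | 1 | 1 | 1 | 3 |

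**2. Number of variables.** Counting measured or derived continuous items in protocol 9.3.2: age, height, weight, BMI (4); time since diagnosis (1); HbA1c (1); systolic and diastolic pressure (2); LVEF (1); four lipids, from "Blood lipids (numeric values for total cholesterol, LDL, HDL, and triglycerides" (4); creatinine, eGFR, UACR (3). The total is 16. The four readings then give 30 × 16 = 480, 14 × 16 = 224, 11 × 16 = 176 and 3 × 16 = 48 tests.

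These totals are soft. For all pairs:

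- Leaving the four demographic variables untested, as SAP 7.1 might imply: 30 × 12 = 360.
- Adding the calculated 10-year SCORE risk: 30 × 17 = 510.
- Eight countries (28 pairs): 37 × 16 = 592.
- Three medication classes (3 pairs): 27 × 16 = 432.

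**3. Chance of at least one nominal p below 0.05, per variable and factor.** Assumptions not in the documents: two-sided alpha 0.05, no true difference between any groups, equal group sizes, large samples. For all pairs this is the upper tail of the studentized range for k groups at 1.96 × √2 = 2.77:

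| Groups | All pairs | One overall test |
|---|---|---|
| 3 | 12.2% | about 5% |
| 4 | 20.3% | about 5% |
| 7 | 44.0% | about 5% |

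The all-pairs range over other assumed alphas is 2.7% / 4.9% / 13.3% at 0.01 and 22.7% / 35.3% / 65.3% at 0.10.

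A separate null simulation (2,000 runs, an assumed 200 normally distributed values per group) gave 12.5%, 18.6% and 43.4% for all-pairs Wilcoxon-Mann-Whitney, and 5.0%, 5.1% and 4.8% for Kruskal-Wallis. These agree within simulation error.

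**4. The protocol's own group targets.** Protocol 9.5 aims for "at least 500 patients in the GLP1a and at least 1000 patients each in the SGLT2i and DPP4i subgroups". At 1000 / 1000 / 500, all pairs gives 12% and Kruskal-Wallis 5%, so unequal class sizes do not alter the picture.

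**5. Single contrast.** Empagliflozin against all others would be one test at 5%.

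**The case against.** The strongest reply is that little depends on this. The primary outcome is descriptive, the tests are an addition to it, and the SAP declares them exploratory and declines correction. Wilcoxon-Mann-Whitney can legitimately be run pairwise. The error rates assume an alpha and a complete null that the plan never states, and they measure a familywise error that it does not claim to control. Protocol 9.9 itself expects drug availability to differ between countries, so the 44% for country is hardly a realistic null. An overall test also does not say which groups differ, although the first objective is a comparison of named treatments.

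Most of this stands as a limit on the size of the point. It does not close the gap. Exploratory status explains the absence of a multiplicity correction; it does not say which test is run on which groups. Pairwise use is possible, but the pairs are not stated.

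For medication one could argue that empagliflozin against everything else is meant, since the rationale in the protocol abstract hints at that contrast. No text defines it, SAP 7 lists four groups, and it would leave specialty and country unresolved.

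A reader might go further and infer that the primary analysis is invalid, that a multiplicity correction is required, or that the SAP has no rule anywhere. The documents support none of these. The descriptive results do not depend on the test, no confirmatory error rate is claimed, and SAP 6.4 and 7.5 are not visible, so absence can be asserted only for the readable text.

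**Conclusion.** The point holds as a mismatch between the named test and the factors it is applied to. For all three factors in SAP 7.3, the test for continuous variables cannot be run without a further choice that no readable text makes. That is more than a missing detail, because the readings run from 3 to 30 tests per variable.

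The consequence is confined to which supplementary p-values are reported, and how many. The test totals and the 12% / 20% / 44% are illustrations under the stated assumptions, not estimates of error in this study. It should be corrected, but it does not threaten the study's main descriptive results.

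**What to change.** In SAP 7 and 7.3, along these lines:

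> Continuous variables will be compared by one Kruskal-Wallis test per factor when the factor has more than two levels (medication, physician specialty, country). Medication has four disjoint groups: empagliflozin, other SGLT2i, DPP4i, GLP-1 RA. The Wilcoxon-Mann-Whitney test is used for two-level factors (history of CV disease) and for the following pairs only: [complete list, for example empagliflozin versus other SGLT2i]. All tests are exploratory and uncorrected.

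Three further points belong with it:

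- **Medication groups.** The list in SAP 7 omits the word other before SGLT2i, leaving it open whether that group contains empagliflozin. Kruskal-Wallis needs groups that do not overlap, so this has to be settled.
- **SAP 7.1 against 7.3.** State which baseline variables are tested and which are only described.
- **Record of the change.** Protocol 9.7.1 and the abstract name only Wilcoxon-Mann-Whitney, so the change should be entered and dated in SAP section 4. SAP Final 3.0 is dated 25 May 2021, after the planned end of data collection in Q1 2021, so the entry should say why the test was changed at that stage.

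Keeping Wilcoxon-Mann-Whitney and listing every pair would also close the gap. The overall test is suggested because it needs one test per factor instead of up to 21.

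The cost is a few sentences in a new SAP version and one log entry, with no new data. The protocol defers detail to the analysis plan, so an amendment should not be needed. The downside is that an overall test does not show which groups differ, and each uncorrected pair added raises the chance of a nominal finding. With one named pair and four equal groups it is about 8% instead of 5%, under the same assumptions.

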7.4 SECONDARY OUTCOME(S)

All analysis will be descriptive and will be performed on PPS.

[figure not shown]
The prevalence of CVD and CKD will be displayed in frequency tables as well as the reasons for treatment choice, concomitant T2D medication and concomitant CVD/CKD medication. Furthermore other physicians involved in the treatment decision as well as the decision to discontinue the treatment will be given.

The "10 year risk for fatal CVD" will be calculated by applying the SCORE Risk Chart (European Society of Cardiology) taking into account patient's age, gender, systolic blood pressure, smoking status, and total cholesterol value at index date 1.

Moreover, the discontinuation rate and the reason for discontinuation will be displayed in frequency tables.

To assess the duration of T2D therapy after one year (\pm 2 months) the time to discontinuation will be analysed by Kaplan-Meier estimates and subgroups will be compared using log-rank test.

For comparison of subgroups, χ^2 -test or Fisher's exact test, if χ^2 -test is not valid, will be used. If the treatment decision depends on socioeconomic factors will be analysed using χ^2 -test or Fisher's exact test.

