7. RATIONALE AND BACKGROUND

Prevalence of diabetes is high with about 425 million of patients worldwide and it is expected that this number will increase to more than 630 million in 2040 (1). Diabetes related complications including micro- and macrovascular complications, which have huge impact on patients' quality of life, as well as healthcare budgets.

The most common cause of mortality in patients with type 2 diabetes (T2D) is cardiovascular disease (CVD), accounting for more than 50 % of deaths and causing an average reduction of life years in a 60 years old male of about 12 years when compared with the general population (1-4). T2D patients have a wide range of cardiovascular (CV) risk factors which not only increase CV mortality but also CV morbidity rates (5-13). Even if diabetes related CV complications have declined with improved standard of care, a substantial burden remains (14) and all-cause mortality is still high in this vulnerable population, significantly reducing life expectancy (3). Also, chronic kidney disease (CKD) is associated with increased all-cause mortality which is substantially higher in patients with a diabetes diagnosis. (15).

While Cardiovascular outcomes Trials (CVOT) on DPP4 inhibitors just confirmed cardiovascular safety but did not provide significant CV benefits over placebo when added to standard of care, data from recent CVOTs with SGLT2 inhibitors and GLP1receptor agonists provided significant cardiovascular benefits (19). Empagliflozin in the EMPA-REG OUTCOME trial and liraglutide in the LEADER trial resulted in lower risk for CV and all-cause mortality when compared with placebo added to standard of care in patients with T2D and established CV disease and/or CV risk factors (17, 18). The number of patients needed to treat to prevent one premature death was 98 patients for 3 years with liraglutide (18) and 39 patients treated for 3 years with empagliflozin (17). Empagliflozin also reduced the risk of hospitalization for heart failure by 35% and was associated with slower progression of kidney disease and renal event rates (17).

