8. RESEARCH QUESTION AND OBJECTIVES

8.1 RATIONALE FOR PERFORMING THE STUDY

Cardiovascular disease (CVD) is the most common cause of mortality in patients with type 2 diabetes (T2D), accounting for more than 50 % of deaths and significantly reducing patients' life expectancy. (1-4). Recent Diabetes and Cardiology guidelines have pointed out that modern antidiabetic drugs like empagliflozin and liraglutide should be used early in the treatment of T2D patients to reduce major adverse CV events and CV mortality (20, 21, 22).

Recent data from Sweden demonstrate a prevalence of CVD in T2D patients as high as 34% (16), while comparable data from CEE countries which would allow raising the awareness on this health topic do not exist. An extrapolation from other European countries to this region, mainly dominated by low income countries with limited healthcare spending will not allow useful conclusions on drug utilization with innovative medications.

In spite of these clear treatment recommendations (20, 21, 22), a recently published US real world study points out that a significant number of patients who would have met the criteria for treatment with drugs like empagliflozin or liraglutide, are not treated according to eligibility criteria (25). The real world use of these drugs based on the Diabetes Collaborative Registry (DCR) was low and these drugs were used mainly in the low-risk diabetes population in which the benefit of CV risk reduction is less likely to happen or was not studied (25).

Knowing the characteristics of T2D patients initiating different treatment for their diabetes can lead to a better understanding for the prescription patterns with modern antidiabetic drugs.

Due to the fact that Diabetes registries or other valid sources, which would allow monitoring of the quality of care in terms of risk factors and the potential complications of diabetes are not available in Central Eastern Europe, there is also a lack of information on patient profiles, receiving prescriptions for modern antidiabetic medications like sodium glucose transporter 2 inhibitor (SGLT2i), dipeptidyl peptidase 4 inhibitor (DPP4i), glucagon like peptide 1 agonist (GLP1a).

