6.3 PATIENT SETS ANALYZED

Prescribed patient set (PPS): All patients fulfilling inclusion and exclusion criteria who have received a first prescription of a respective study medication.

Full Analysis set (FAS): All patients from PPS with documentation at index date 2. Patients included before the protocol amendment need an additional signed informed consent at index date 2.

Table 6.3: 1 Patient sets analyzed

Class of outcome	Patient set	
	PPS	FAS
Primary and secondary outcomes at index date 1	X	
Secondary outcomes at index date 2		X

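### The SCORE-based 10-year fatal-CVD risk takes no account of diabetes or established CVD, so it should not be reported as the absolute risk of this cohort

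*SAP*

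**What the plan says.** SAP 7.4 states that the 10-year fatal-CVD risk "will be calculated by applying the SCORE Risk Chart (European Society of Cardiology) taking into account patient's age, gender, systolic blood pressure, smoking status". The fifth input there is total cholesterol, also taken at index date 1. Protocol 9.3.2, item 4, lists the same measure among the risk factors, "taking into account patient's age, gender, systolic blood pressure, smoking status, and total cholesterol value at index date". Diabetes and previous CVD are not inputs in either place.

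On the population, SAP 7.4 says of the secondary outcomes: "All analysis will be descriptive and will be performed on PPS". SAP 6.3 defines that set as "All patients fulfilling inclusion and exclusion criteria who have received a first prescription of a respective study medication". A T2D diagnosis is inclusion criterion 3 (Protocol 9.2.1), and the exclusion criteria (Protocol 9.2.2) do not mention CVD. Under SAP 6.6 nothing is imputed, and a patient with a missing value is left out of the outcome concerned.

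Established CVD is defined in Protocol 8.2 by six conditions, each recorded as a yes/no item in Protocol 9.3.2. SAP 5.2 uses it to split the description of treatment, and SAP 7 plans subgroup analyses by CV history, medication, country and physician specialty.

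**The concern.** The output is named as an absolute 10-year risk of death from CVD, but its inputs omit the disease that defines the cohort and the history that defines one of its main subgroups. CVD risk factors belong to a named secondary outcome (Protocol 9.3.2, SAP 5.2). Protocol 8.1 also asks, as background, whether these drugs go mainly to lower-risk patients.

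A score that cannot see previous CVD is a poor instrument for that question. Compared by CV history, it shows only how the two groups differ in age, gender, systolic pressure, smoking and cholesterol. Compared by drug, it gives no credit to a drug group for containing more patients with established CVD. Treatment after an event may also lower pressure and cholesterol, which could shrink the contrast between patients with and without CVD.

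**Working it through.** The plan states no expected SCORE value, so there is no figure to reproduce. The check sets the inputs against the population, counts the patients concerned, and asks what can be said about size.

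1. **Inputs against population.** Write the score as S = f(age, gender, systolic pressure, smoking, total cholesterol). T2D status is the same for everyone and does not enter f. CVD status varies between patients and does not enter f either. Neither document shows a multiplier, a separate risk category or a restriction.

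2. **Consequence for two patients.** Let A have a previous infarction and B no CVD, with the same five values. Then S(A) = S(B), a difference of 0, whatever A's history.

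3. **Consequence for two groups.** The mean of S depends only on the distribution of the five inputs. Suppose two drug groups share that distribution, with 50% and 25% established CVD (assumed shares). The difference in mean score is again 0.

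4. **How many patients.** The planned size is about 4,000 (Protocol 9.5). The only prevalence in the documents is in Protocol 8.1: "Recent data from Sweden demonstrate a prevalence of CVD in T2D patients as high as 34" per cent. With that figure as an assumption for this region:
   - 0.34 × 4,000 = 1,360 patients with CVD that the score ignores.
   - Assumed range: 0.20 × 4,000 = 800 and 0.50 × 4,000 = 2,000.
   - If a share m of these patients lacks at least one input, the count is 1,360 × (1 − m). For example, m = 10% (assumed) gives 1,360 × 0.90 = 1,224. The documents give no value for m.

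5. **Direction and size.** Let p be the CVD prevalence. Let R_T and R_C be the risk multipliers for T2D and for established CVD, beyond what the five inputs carry. If the inputs are unrelated to CVD status, then

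   true mean risk / reported mean risk = R_T × [(1 − p) + p × R_C].

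   With R_T = R_C = 1 the ratio is 1. If neither multiplier is below 1 and at least one exceeds 1, the ratio is above 1 for any p between 0 and 1. The documents give neither multiplier. Protocol 7 describes CVD in T2D as "accounting for more than 50 % of deaths and causing an average reduction of life years in a 60 years old male" of about 12 years relative to the general population. That makes a ratio above 1 likely, but the comparison is not conditional on the five inputs and gives no value for R_T or R_C.

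**The case against.** The strongest reply has four parts.

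- **The chart is not in the documents.** SAP 8 only cites the 2016 European prevention guideline. Whether a chart value is too low in T2D depends on how the chart was calibrated, which the documents do not say. Protocol 7 also notes that T2D patients carry many CV risk factors, so part of their excess risk may already enter through the five inputs. This stands. A reader might infer that the risk is understated for every patient, or by a known factor; the documents support neither.
- **CVD is reported directly elsewhere.** The six conditions are collected, CVD prevalence is tabulated, and treatment with and without established CVD is a separate secondary outcome. A reader of the report would see CVD by drug. This limits the harm, and a false conclusion that the drugs go to low-risk patients is a possibility, not a prediction. But tabulating CVD separately does not correct a score carrying the name of an absolute risk.
- **The counts are soft.** Patients lacking an input are not scored, so a reader should not infer that all 4,000 are affected. The 34% is Swedish, and Protocol 8.1 itself warns against extrapolating from other European countries to this region. Both points stand.
- **The item is small and the text incomplete.** The score is one descriptive risk factor in an analysis called exploratory, and its inputs are openly listed. SAP 6.4 and 7.5 have no visible title or text, so one can say only that no rule is visible.

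A reader might also suspect use outside the chart's age limits, since eligibility starts at 18. The documents give no such limits, so that is not part of this point.

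**Conclusion.** The point holds in a limited form. As written, the score cannot separate patients with and without established CVD who share the five inputs, and it has no term for the T2D that all patients have. This follows from the listed inputs and the analysis set alone. The score should therefore not be read as the absolute fatal-CVD risk of the cohort, nor compared by CV history or drug on that footing.

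Understatement is a reasonable inference from Protocol 7, but no size can be attached to it. The number of patients whose CVD is ignored is up to about 1,360 of 4,000, fewer after missing inputs. It rests on applying the Swedish prevalence to this region.

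This is a cheap improvement to a descriptive secondary item. Study size, error rates and the discontinuation analysis are unaffected, and the primary outcome does not depend on it.

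**What to change.** In SAP 7.4 and Protocol 9.3.2:

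- compute SCORE only in patients without established CVD, using the definition already in Protocol 8.2;
- show patients with established CVD as a separate category, without a score;
- label the remaining values 'SCORE from five risk factors, not accounting for diabetes', and do not describe them as the cohort's absolute 10-year fatal-CVD risk.

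The change needs revised wording in two places and one programming filter on comorbidity items already collected. No new data are required. The price is that fewer patients are scored: at 34% prevalence, at most 4,000 − 1,360 = 2,640 before missing inputs. For diabetes the remedy is only a label: it prevents misreading but does not correct the value.
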